5.19 Subject Replacement

Subjects who undergo Early Discontinuation after randomization and before vaccine administration may be replaced by randomizing an additional subject at the Sponsor's discretion. Subjects who undergo Early Discontinuation after study vaccination will not be replaced.

5.20 Study Completion: Overall

The study is planned to be completed after all subjects have completed the Month 6 visit (or Early Discontinuation, as appropriate), all necessary safety follow-up has been completed, and all data have been monitored and queries have been resolved. The Sponsor reserves the right to terminate the study prior to the planned study completion.

6 STUDY PROCEDURES BY VISIT

The overall summary of procedures and assessments by visit is given in the Schedule of Events in [APPENDIX A](#) and [Guidance for Industry, Toxicity Grading Scale, 2007](#). All visits are relative to the day of vaccine administration, Day 1. Acceptable time windows for the visit schedule are indicated.

6.1 Scheduled Study Visits

6.1.1 Screening (-30 days to Day 1)

The following will take place during the visit, which will occur within 30 days prior to and including Day 1:

- Informed consent
- Collection of demographics
- Review of eligibility criteria
- Collection of medical history
- Physical exam
- Vital signs
- Collection of prior and concomitant medications

Screening and Day 1 procedures may be completed on the same day.

6.1.2 Day 1

The following will take place during the visit and *prior* to study vaccine administration:

- Collection of updated medical history, if applicable
- Confirmation Inclusion/Exclusion criteria are met
- Targeted physical examination, if indicated by updated medical history
- Vital signs
- Blood collection (pre-dose) for serum sample for immunogenicity
- Review of prior and concomitant medications
- Randomization

All eligible, consented, and randomized subjects will be vaccinated at the Day 1 visit.

- Study vaccine administration, either VAX-24 or PCV20

The following will take place during the visit and *after* study vaccine administration:

- Acute observation for at least 30 minutes after vaccine administration
- Vital signs collected at least 30 minutes after vaccine administration
- AE (solicited and unsolicited) and SAE evaluation
- Review of concomitant medications
- Instructions on completion of a diary, use of a ruler and thermometer

6.1.3 Day 8 (+3 days)

The following procedures will take place at this visit:

- Review of diary data with the subject; Investigator's assessment of severity and relationship to study vaccine
- Review of concomitant medications
- AE (solicited and unsolicited) and SAE evaluation

6.1.4 Day 29 (\pm 3 days)

The following procedures will take place during this visit:

- Review of concomitant medications
- AE (unsolicited) and SAE evaluation
- Blood collection for serum sample for immunogenicity

6.1.5 Months 3 and 6 (90 to 180 days after Day 1 (\pm 5 days))

These visits are follow-up phone calls for safety evaluation. The following procedures will take place at each visit:

- SAE, NOCI, and MAAE evaluation
- Review of concomitant medications associated with SAEs, NOCIs, MAAEs, or prohibited medications

6.2 Early Discontinuation Visit

All subjects who discontinue study participation before the Month 6 visit will be requested to undergo an Early Discontinuation visit.

If the visit occurs within 7 days after study vaccine administration, the following will be conducted:

- Review of diary data with the subject; Investigator's assessment of severity and relationship to study vaccine

- Review of unsolicited AEs and SAEs
- Review of concomitant medications associated with new or ongoing AEs and any SAEs
- Blood collection for serum sample for immunogenicity

If the visit occurs after Day 8 and before Day 29, the following will be conducted:

- Review AEs and SAEs
- Review concomitant medications associated with new or ongoing AEs and any SAEs
- Blood collection for serum sample for immunogenicity

6.3 Unscheduled Visits

Any study procedure, excluding study vaccination, may be conducted at an unscheduled visit as needed. Examples may include repeat physical examination, vital signs, blood collections, and additional safety follow-up for an AE.

7 SAFETY

7.1 Definitions

7.1.1 Adverse Event

An adverse event is any untoward medical occurrence in a study subject, regardless of the suspected causal relationship with study vaccine.

The definition of an AE includes:

- A new-onset symptom or disease
- An exacerbation of a pre-existing symptom or disease
- A new-onset laboratory abnormality considered by the Investigator to be clinically significant
- A new-onset symptom or disease that occurs as a result of a protocol-specified procedure

The definition of an AE does **not** include:

- A pre-existing symptom or disease that does not worsen during the study (even if first disclosed by the subject after the start of the study)
- A medical or surgical intervention such as surgery, endoscopy, tooth extraction, or transfusion (although the condition leading to the procedure or a complication from the procedure may be an AE)
- An uncomplicated pregnancy
- A dosing error without any resulting signs or symptoms
- Any other situation where an untoward medical occurrence has not occurred (eg, hospitalization for cosmetic elective surgery or social admissions)

The definition of a treatment emergent AE (TEAE) is an event that occurs after vaccination and within the 28 days after vaccination (ie, excluding those after a subject has given informed consent, but before vaccination).

The definition of a NOCI includes:

A new onset of chronic illness is a disease or condition, which is newly diagnosed, requires ongoing medical attention and/or limits activity of daily living (eg, heart disease, cancer, diabetes).

The Investigator will attempt to establish a diagnosis based on signs, symptoms, and other clinical information. Whenever possible, the Investigator will report an AE as a diagnosis rather than one or more signs or symptoms. If a clinically significant laboratory abnormality meets the

definition of an AE, a diagnosis or clinical signs and symptoms rather than the abnormal laboratory finding should be reported if possible. If no diagnosis is known and clinical signs and symptoms are not present, but the laboratory abnormality is clinically significant by itself, then it should be reported as the AE.

7.1.2 Solicited Adverse Event

A solicited AE is a protocol-specified AE about which the Investigator or designee proactively asks the subject during a protocol-specified period. Solicited AEs for this study are local events of pain, erythema (redness) and edema (swelling) at the injection site, and systemic events of fever (oral temperature $\geq 100.4^{\circ}\text{F}$), fatigue, headache, muscle pain, and joint pain.

7.1.3 Unsolicited Adverse Event

An unsolicited AE is an AE that is spontaneously reported by the subject or discovered by the Investigator. New onset of chronic illness(s) would be recorded as part of the collection of unsolicited AEs as specified in the visit procedures. Unsolicited AEs will be collected separately from solicited AEs.

7.1.4 Serious Adverse Event

An SAE is an AE (either solicited or unsolicited) which meets any of the following criteria:

- Results in death
- Is life-threatening
- Requires hospitalization or prolongs an existing hospitalization
- Results in a persistent or significant incapacity or substantial disruption of the ability to conduct normal life functions
- Is a congenital anomaly or birth defect
- Important medical event that may jeopardize the patient or subject and/or may require medical or surgical intervention to prevent one of the above outcomes

The Investigator will evaluate all AEs for seriousness using the above criteria.

“Life-threatening” means that, in the opinion of the Investigator, the subject was at immediate risk of death from the event as it occurred. It does not mean that the event might have caused death had it occurred in a more severe form.

Hospitalization for observation or for elective treatment of a pre-existing condition that did not worsen during the study is not considered an SAE.

Important medical events may be considered serious at the discretion of the Investigator.

These seriousness criteria also apply to the Study Stopping Rules in [Section 7.9](#).

7.2 Severity Grading

The Investigator will grade all AEs for severity. AEs listed in the [Guidance for Industry, Toxicity Grading Scale for Healthy Adult and Adolescent Volunteers Enrolled in Preventive Vaccine Clinical Trials, September 2007](#) will be graded according to the criteria in the table. AEs not listed in the Toxicity Grading Scale will be graded as follows:

- Mild (Grade 1) – No interference with activity
- Moderate (Grade 2) – Some interference with activity
- Severe (Grade 3) – Significant; prevents daily activity
- Potentially Life-Threatening (Grade 4) – ER visit or hospitalization

7.3 Causality Assessment

The Investigator will assess all AEs, including solicited AEs, for causality (relationship to study vaccine), assigning one of these three categories: Not Related, Possibly Related, or Probably Related.

An AE will be considered “Not Related” to study vaccine if **any** of the following conditions are met:

- An unreasonable temporal relationship between administration of the study vaccine and the onset of the AE (eg, the event occurred either before, or too long after, administration of the study vaccine for it to be considered related).
- A causal relationship between the study vaccine and the AE is biologically implausible (eg, injury as a passenger in an automobile accident).
- A clear alternative causality for the AE is present (eg, typical adverse reaction to a concomitant medication).

An AE will be considered “possibly related” if there is a reasonable possibility that the AE may have been caused by the study vaccine.

- A single occurrence of an event that is uncommon and known to be strongly associated with vaccine exposure (eg, angioedema, hepatic injury, Stevens-Johnson Syndrome)
- One or more occurrences of an event that is not commonly associated with vaccine exposure, but is otherwise uncommon in the population exposed to the vaccine (eg, tendon rupture)
- An aggregate analysis of specific events observed in a clinical trial (such as known consequences of the underlying disease or condition under investigation or other events that commonly occur in the study population independent of vaccine administration) that

indicates those events occur more frequently in the vaccine treatment group than in a concurrent or historical control group

An AE will be considered “Probably related” if there is evidence that the AE was caused by the study vaccine.

7.4 Follow-up of Adverse Events

The Investigator must follow all AEs until resolution, until the condition stabilizes or is no longer clinically significant, or until the subject is lost to follow-up.

The Investigator is responsible for ensuring the conduct of any supplemental investigations considered necessary to evaluate the AE. These may include additional laboratory tests or investigations, histopathological examinations, or consultation with other health care professionals.

In the event of a non-fatal SAE, subjects will be instructed to contact the Investigator (or designee) immediately. All subjects experiencing an SAE will be evaluated by the Investigator or designee as soon as is feasible following the report of the SAE by the subject. In the event of a fatal SAE, the Investigator must provide the Sponsor with any available post-mortem findings, including histopathology.

Additionally, the Sponsor may request that the Investigator perform or arrange for the conduct of supplemental investigations for one or more AEs.

7.5 Reporting of Adverse Events

[figure not shown]
7.5.1 Reporting Periods

The four reporting periods for solicited AEs begin immediately after study vaccine administration and continue for 7 days after the injection. The reporting period for unsolicited AEs is immediately after study vaccine administration on Day 1, continuing through Day 29. AEs that correspond to solicited AE terms but occur outside of (or continue past) the solicited AE collection periods are also collected through the unsolicited AE reporting periods. The reporting period for SAEs begins at the time of informed consent and continues for the duration of study participation.

A summary of the reporting periods is presented in Figure 2.

Figure 2 Safety Events Reporting Periods

7.5.2 Documentation

The Investigator or designee will document all AEs in the subject's source documents and solicited AEs into the source document file within 24 hours of awareness.

All AEs should include:

- Event term
- Start and stop date
- Severity
- Seriousness (Yes/No) and if yes, which Seriousness criteria were met
- Relationship to Study Vaccine
- Action taken in response to the AE
- Action taken with Study Vaccine

7.6 SAE Reporting

The Investigator or designee must report all SAEs to the Vaxcyte Clinical Safety Team, within 24 hours of becoming aware of the event, using the SAE Report Form. The Investigator or designee must also enter SAEs into the source document.

E-mail transmission of the SAE Report Form is the preferred method to transmit this information to the Vaxcyte Clinical Safety Team. If initial notification is provided via telephone, this does

not replace the need for the Investigator to complete and sign the SAE Report Form within the designated reporting time frames.

Communication Methods to the Vaxcyte Clinical Safety Team:

E-mail (primary): [contact]

Telephone (emergency): [contact]

The SAE Report Form should be completed as thoroughly as possible and be signed by the Investigator or designee before reporting to Vaxcyte. The SAE Report Form must include an assessment of causality and should include a preliminary diagnosis if possible. All SAEs assessed as not related must include an alternate causality.

To avoid delays in initial reporting, additional information regarding the SAE may be provided as a follow-up report. The Investigator may also modify the diagnosis, seriousness, and/or causality assessment based on this information.

Vaxcyte will notify the Investigator of SAEs that meet criteria for expedited reporting to regulatory authorities. The Investigator is responsible for notifying the applicable IRB of these events and adhering to any other applicable local reporting requirements.

The Sponsor will report AEs to FDA in accordance with 21 CFR 312.32. Specifically, the Sponsor will report unexpected fatal or life-threatening suspected adverse reactions no later than 7 days after initial receipt of the information, and serious and unexpected suspected adverse reactions (SUSARs) no later than 15 calendar days after determining that the information qualifies for expedited reporting.

It is also the responsibility of Vaxcyte to make the determination of which SAEs are SUSARs, as defined in 21 CFR 312.32.

- *Suspected adverse reaction* means any AE for which there is a reasonable possibility that the drug caused the AE.
- *Unexpected adverse reaction* means an AE that is not listed in the Investigator's Brochure or is not listed at the specificity or severity that has been observed.

All SUSARs, as agreed upon by the Sponsor, will be reported to FDA. SUSARs will be provided to all participating Investigators by Vaxcyte.

7.7 Medical Monitor

[figure not shown]
The Medical Monitor will be the first point of contact regarding safety and eligibility questions for the study and will work closely with the Sponsor Medical Director to assess subject

eligibility, AEs and SAEs that trigger the stopping rules, and all other safety related questions from the sites.

The Sponsor Medical Director will provide oversight for the study, review blinded safety data, subject eligibility, and assess causality of SAEs on an ongoing basis.

7.8 Data Monitoring Committee

The DMC will consist of two persons (independent Subject Matter Experts) and an unblinded statistician to compile the data and present to the members. The DMC will independently conduct ad hoc reviews if the study is paused, triggered by one of the Stopping Rules, to identify any emerging safety concerns. Stopping rules will be observed during the active study vaccine administration period (see [Section 7.9](#)).

For further information regarding DMC, refer to the DMC Charter.

7.9 Study Stopping Rules

During the vaccination period(s), if any of the stopping rules are triggered, no further administration of study vaccine(s) will occur until safety data are reviewed by the DMC in communication with the Medical Director and the Investigator at the site where the event occurred, as needed. Study dosing may be resumed if the DMC determines it is safe to proceed with no modifications or with modifications to the protocol plans.

- One (1) SAE assessed as at least possibly related to investigational product
- One (1) or more subjects with a Grade 4 (potentially life threatening) AE assessed as at least possibly related to investigational product

- Two or more subjects with the same or similar Grade 3 (severe) AE assessed as at least possibly related to investigational product

The appropriate regulatory authority will be informed in writing when either of the following occurs:

- Study dosing is stopped
- DMC has recommended to resume or discontinue study enrollment

Enrollment may be resumed following review of available safety data by the DMC.

Vaxcyte clinical safety team will refer to the VAX24-102 Safety Medical Monitoring Plan for detailed procedures on stopping rule reporting and safety oversight for the study.

8 DATA HANDLING

8.1 Source Documentation

The Investigator must maintain source documentation of all study conduct data and observations relevant to the study. This source documentation includes, but is not limited to, ICFs, original medical records, progress notes from the Investigator and study staff, laboratory reports, diary for solicited AEs, and documentation of study vaccine accountability.

8.2 Retention of Study Documentation

The Investigator will maintain all study documentation, including copies of ICFs, source documentation, and documentation of study vaccine accountability, for either 2 years following FDA or other regulatory approval of VAX-24, or 2 years after clinical development of VAX-24 is discontinued, unless a longer period is required by applicable law or regulation. The Investigator will destroy study documentation only upon instruction by the Sponsor and must notify the Sponsor upon completion of such destruction. Subject identity information will be maintained for 15 years unless a longer period is required by applicable law or regulation.

8.3 Data Monitoring

The Sponsor or designee will monitor completed source documents at regular intervals throughout the study to verify adherence to the protocol; completeness, accuracy, and consistency of the data; and adherence to local regulations on the conduct of clinical research. The Investigator must make source documentation accessible to the Sponsor or designee as needed to verify the information in the source documents. The Investigator agrees to cooperate with the Sponsor or designee to ensure that any problems detected during data monitoring are resolved.

8.4 Audit Compliance

The Investigator must permit the Sponsor and/or designee, regulatory agencies, and/or the IRB direct access to facilities and study documentation for the purpose of auditing study conduct. Direct access includes examining, analyzing, verifying, and reproducing any records and reports that are needed for the evaluation of the study.

9 STATISTICAL ANALYSIS

This Phase 2 study is designed to achieve both safety and immunogenicity objectives.

Descriptive summaries of variables by treatment will be provided. For continuous variables, the number of non-missing values (n) and the median, mean, standard deviation, minimum, and maximum will be tabulated by treatment. For categorical variables, the counts and proportions of each value will be tabulated by treatment. Confidence intervals (CIs) will be provided as appropriate. All statistical comparisons will be tested at two-sided 0.05 levels of significance.

A statistical analysis plan will be generated and approved prior to the data freeze and treatment group unblinding for the primary safety and secondary immunogenicity endpoints through Day 29 visits. Individual treatment unblinding will occur after the data is cleaned through the last Month 6 visits and final database lock. A single completed Clinical Study Report (CSR) will summarize safety findings through Month 6 for all subjects.

9.1 Sample Size Calculation

The sample size is not driven by statistical assumptions for formal hypothesis testing but was based on the safety objective for the study. A total of 200 subjects should provide sufficient information to assess safety and immunogenicity. The sample size will also be adequate to establish variance of immune response in this target population and plan future studies.

9.2 Treatment Period

The Treatment period begins at the time of study vaccine administration and extends through the Day 29 visit. The Follow-up period spans the time following the Day 29 visit through Month 6 (after study vaccine administration).

9.3 Populations for Analysis

Randomized Population: All screened subjects who provide informed consent, provide demographics, other baseline and screening measurements, are randomized, and are assigned a study subject ID (number). Each subject will be analyzed as randomized (i.e., according to the vaccine regimen to which the subject was randomized).

Exposed Population: All subjects who receive the study vaccination.

Safety Population: All subjects in the Exposed Population who provide safety assessment data. This includes any subjects not lost to follow-up at Day 1, as they will be at risk for reporting an SAE. Each subject will be analyzed as treated (i.e., according to the vaccine regimen a subject received, rather than the vaccine regimen to which the subject may have been randomized).

Immunogenicity Evaluable Population (IEP): The immunogenicity population will be analyzed as treated (i.e., according to the vaccine regimen a subject receives, which may be different from the vaccine regimen to which the subject is randomized in the case of treatment errors).

The IEP includes all subjects in the Exposed Population who:

- Have no major protocol deviation that would impact immunogenicity assessment or other reason to be excluded as defined prior to unblinding or analysis.
- Have not received a prohibited medication or vaccine.
- Provide evaluable serum sample results for baseline, the relevant post-vaccination time points, and within the required time frames:
 - Baseline: Day 1 or within 30 days before first study vaccine administration
 - Day 29: Day 26 through Day 34, inclusive

9.4 Demographic and Baseline Characteristics Analysis

The demographic and baseline characteristics will be summarized descriptively according to treatment group. Age, height, weight, and body mass index at enrollment will be summarized by reporting the mean, standard deviation, median, minimum, and maximum. The frequencies and percentages of subjects by sex, race, and ethnicity will be presented.

Demographic data will be tabulated for the Randomized, Immunogenicity Evaluable, and Safety Populations.

9.5 Safety Analysis

All safety analyses will be based on the Safety Population.

9.5.1 Analysis of Extent of Exposure

The frequencies and percentages of subjects with vaccinations will be summarized by treatment group for the Randomized Population.

9.5.2 Solicited AEs

Except for redness and swelling, all solicited AEs (local and systemic) will be summarized according to severity grading scales defined in [Section 7.2](#), from “mild” to “potentially life-threatening.”

Solicited AEs will be recorded daily until 7 days post-injection within a diary. The analyses of solicited AEs will be performed by maximum severity and by treatment group. In addition, solicited AEs ongoing after 7 days post-injection will also be recorded as unsolicited AEs.

Frequencies and percentages of subjects experiencing each solicited AE will be presented by maximum severity. Summary tables showing the occurrence of any local or systemic solicited AE overall and at each time point will also be presented.

The severity of redness and swelling recorded as diameters (cm) will be summarized according to categories based on the largest diameter linear measurement when the local reaction is present:

- Grade 0/absent: 0 - 2.4 cm
- Grade 1/mild: > 2.5 - 5.0 cm.
- Grade 2/moderate: > 5.1 - 10.0 cm.
- Grade 3/severe: > 10.0 cm.

The following summaries of subjects will be performed:

- Solicited events by day post-injection, for each event and for any event.
- Time of onset of solicited AEs, after injection, for each event and any event.
- Solicited AEs by maximum event severity, after injection, for each event and for any event.
- Duration of solicited AEs, after injection, for each event and maximum duration of any event.
- Solicited AEs, occurrence of at least one event by category (local, systemic), after injection.

For each of the time points or time intervals presented in the summaries, only subjects with at least one observation (i.e., any non-missing values but excluding “Not done/unknown”) for the solicited AEs will be summarized.

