5.10 Solicited Adverse Events

Solicited AEs will be collected for 7 days, after the injection, starting on Day 1. Solicited AEs for this study are local events of pain, erythema (redness) and edema (swelling) at the injection site, and systemic events of oral temperature $\geq 100.4^{\circ}\text{F}$, fatigue, headache, muscle pain, and joint pain.

Subjects will receive and be trained on the use of a paper diary to observe, measure, and record these solicited AEs. The diary will serve as the primary source document and data will be entered by the site into the subject visit solicited AE form in the EDC system. A digital thermometer will be provided to the subject to measure oral temperature each day, and it is to be recorded daily in the diary. To record injection site local reaction, a ruler will be provided to the subject to measure the diameter of redness and swelling at the largest point of the reaction each day; it is to be recorded daily in the diary.

Subject is to be instructed to immediately call the study site if they experience a grade 3 (severe) or grade 4 (life threatening) symptom. Study site will determine if the subject needs to return to the site for safety evaluation and follow-up.

Study staff will review the signs and symptoms recorded in the diary and the action taken for the event during the subject's next scheduled clinic visit (Day 8). The Investigator will assess all recorded solicited events for severity and relatedness during this subject visit. Severity will be graded according to the FDA Toxicity Grading Scale (FDA 2007). The results of the Investigator's assessment, if different from the subject's entry, will be recorded in a separate field specified for Investigators within the EDC system.

Symptoms continuing beyond the solicited AE collection period (7 days following the injection) will be collected and recorded as an unsolicited AE in the source document.

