6.4.1. Adverse Events

6.4.1.1. Solicited Adverse Events

Solicited AEs are protocol-specified local and systemic symptoms/events that are proactively collected from the subject and evaluated by the Investigator or designee. Solicited AEs are collected for 7 days after each injection, starting on Day 1, within an electronic diary.

Solicited AEs for this study are:

- Local events: Pain, Erythema (redness) at the injection site, Edema (swelling) at the injection site
- Systemic events: Fever (oral temperature $\geq 100.4^{\circ}\text{F}$), Fatigue, Headache, Muscle pain, Joint pain

The Subject and the Investigator will grade all AEs for severity from "mild" (grade 1) to "potentially life-threatening" (grade 4), except for severity of redness and swelling recorded as diameters (cm) and graded accordingly (see Guidance for Industry Toxicity Grading Scale for Healthy Adult and Adolescent Volunteers Enrolled in Preventive Vaccine Clinical Trials, September 2007 for details on grading scale).

Only Solicited AEs collected in the diary CRF, within 7 days after vaccine administration (i.e. from Day 1 to Day 7) will be analyzed in this Section. Occurrence of a solicited AE on a specific Day will be identified by a Grade ≥ 1 for that AE on that day.

Solicited AEs continuing beyond 7 days after injection will be combined with unsolicited AEs and described separately as specified in Section 6.4.1.3.

The following characteristics will be calculated:

- Maximum severity (Investigator):

For each solicited AE collected for a subject, the maximum severity will be the highest grade recorded, as per Investigator, for all occurrences of this AE within 7 days of vaccine administration (i.e., from Day 1 post-administration to Day 7) for the overall summary, or within a single day for the summary by day. There will be no replacement in case of missing severity.

- Maximum relationship (Investigator):

For each unsolicited AE collected for a subject, the maximum relationship will be the strongest relationship, as per Investigator, for all occurrences of this AE. There will be no replacement in case of missing relationship.

- Time of first onset of first event (days):

Day of onset of the first solicited AE, as per the nominal visit where the first solicited AE was first reported (as per Investigator). This will range from 1 (Day 1 = Day of study vaccine administration) to 7 (Day 7).

- Duration of solicited AEs (days):

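### The Protocol 9.5.2 diameter bands for redness and swelling leave 2.5 cm and 5.1 cm without a grade, and the documents do not settle whether these bands or an external scale govern the tables (minor)

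*Protocol*

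**What the plan says.** Protocol 9.5.2 takes two local reactions out of the general severity scale: "Except for redness and swelling, all solicited AEs (local and systemic) will be summarized according to severity grading scales defined in" Section 7.2. It then lists diameter categories for them: "Grade 0/absent: 0 - 2.4 cm", "Grade 1/mild: > 2.5 - 5.0 cm", "Grade 2/moderate: > 5.1 - 10.0 cm", and Grade 3 for anything above 10.0 cm.

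The diameters come from the subject. Under Protocol 5.10, "a ruler will be provided to the subject to measure the diameter of redness and swelling" each day, at the largest point. Neither document gives a reading precision or a rounding rule.

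Other places refer to a different source for the grades. Protocol 5.10 says "Severity will be graded according to the FDA Toxicity Grading Scale (FDA 2007"), and Protocol 7.2 sends every event listed in that 2007 guidance to its table. SAP 6.4.1.1 has subject and Investigator grade events from mild to potentially life-threatening, "except for severity of redness and swelling recorded as diameters (cm) and graded accordingly", and points to the same guidance for detail. The SAP neither prints nor cites the 9.5.2 bands, and neither document prints the guidance's diameter limits.

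The grade then defines the event. In SAP 6.4.1.1, "Occurrence of a solicited AE on a specific Day will be identified by a Grade" of 1 or more on that day, and duration runs from the first such day to the day on which the grade is 0 again. Redness and swelling are named components of the first primary safety endpoint (Protocol 2.1, SAP 3.2).

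**The concern.** A category list that feeds a primary endpoint should put every possible measurement in exactly one category. This one does not, and its first gap lies on the boundary between no event and event. Because the SAP uses the grade alone to decide whether a reaction occurred and when it ended, a diameter without a grade has no defined status in the occurrence, maximum-severity or duration summaries. Half a centimetre is a natural mark on a ruler, so 2.5 cm is a plausible diary entry.

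The reference to an external scale might remove the problem, but the documents do not say how that scale relates to the 9.5.2 list. As the text stands, whoever programs the tables chooses the source of the grades and, if the choice is 9.5.2, how to close its gaps.

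**Working it through.** The plan states no figure on this point, so there is none to reproduce. The check applies the four printed bands literally to diameters from 0 to 15 cm.

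**Inputs.** From Protocol 9.5.2, with d the largest diameter in cm:
- Grade 0 if 0 ≤ d ≤ 2.4
- Grade 1 if 2.5 < d ≤ 5.0
- Grade 2 if 5.1 < d ≤ 10.0
- Grade 3 if d > 10.0

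From SAP 2.3: 50 subjects per arm. From SAP 6.4.1.1: event on a day if the grade is at least 1.

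**Step 1: which values have no grade?** On a continuous scale they are 2.4 < d ≤ 2.5 and 5.0 < d ≤ 5.1. No value falls in two grades. By assumed reading precision:

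| Reading step | Values with no grade |
|---|---|
| 1 cm | none |
| 0.5 cm | 2.5 |
| 0.25 cm | 2.50 |
| 0.1 cm | 2.5, 5.1 |
| 0.05 cm | 2.45, 2.50, 5.05, 5.10 |

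**Step 2: what does the SAP event rule do with them?** Read literally, 5.0 cm is Grade 1 and counts, 5.1 cm has no grade and does not count, and 5.2 cm is Grade 2 and counts. For duration, suppose a reaction measures 3.0 cm on Day 2, 2.5 cm on Day 3 and 2.0 cm on Day 4. Its grades are 1, none and 0. The Day 3 reading neither continues the event (Grade 1 or more) nor ends it (Grade 0).

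**Step 3: size in one row of the table.** One subject in an arm of 50 is 1/50 = 2.0 percentage points. The denominator does not change. Protocol 9.5.2 and SAP 6.4.1.1 keep every subject with at least one non-missing observation, and a recorded diameter is an observation. The effect is therefore on the numerator only.

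Illustration, with assumed counts: 10 of 50 subjects have redness, and m of the 10 have no qualifying reading other than an ungraded one.
- All graded as events: 10/50 = 20%
- Bands read literally, (10 − m)/50: m = 1 gives 18%, m = 2 gives 16%, m = 3 gives 14%

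**Step 4: size for any local reaction.** The same subject may already count through another day, the other measured reaction, or pain. The change per subject is therefore 0 or 2.0 points, never more.

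**The case against.** The strongest reply is that the gap may never reach a table. SAP 6.4.1.1, the text a programmer works from, does not use the 9.5.2 bands and refers to the 2007 guidance, as do Protocol 5.10 and 7.2. This stands. It makes the effect on results conditional, and leaves two sources of diameter grades with no rule for choosing between them.

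A second reply is that the intent is plain. The limits step by 0.1 cm (2.4 then 2.5, 5.0 then 5.1), so reading the first two strict signs as 'from' closes both gaps at 0.1 cm readings. That reading is likely but not stated. In the same list the Grade 3 sign is properly strict, since Grade 2 ends at 10.0 cm. Even on the kinder reading, 2.45 and 5.05 cm remain ungraded if readings are recorded to 0.05 cm.

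A reader might also infer three stronger points that the documents do not support.
- *That the SAP has replaced the protocol's scale without declaring it in SAP section 7.* The guidance's limits are not printed, so a difference cannot be shown. The SAP sets redness and swelling apart while still citing the guidance, so the similar exception in 9.5.2 may mean only that these two are graded from diameters.
- *That subjects with ungraded readings drop out of the denominator.* The rule on non-missing observations keeps them in.
- *That the Investigator's severity field, described in Protocol 5.10 as recording a differing assessment, is blank on agreement, so that agreed events are lost.* Protocol 5.10 has the Investigator assess every recorded solicited event, and SAP 6.4.1.1 has both parties grade all events, which points to a filled field. The case report form and its completion guidelines are not included, and part of the SAP is blacked out. The planned by-day table on the subject's own severity would expose such a loss. It is a question for the sponsor, not an error shown by the text.

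**Conclusion.** The printed list is defective: two intervals of diameter, 2.4 to 2.5 cm and 5.0 to 5.1 cm (lower limits excluded, upper included), have no grade. That much follows from the text alone. Any effect on results requires that the 9.5.2 bands, rather than the cited scale, be programmed as printed, that readings be finer than whole centimetres, and that some subjects have no other qualifying reading. Under those assumptions each such subject changes one redness or swelling row by at most 2.0 percentage points, and the any-local-reaction percentage by no more. How many there will be cannot be known from the documents. It would go too far to say that the primary endpoint will be miscounted. What is established is a boundary error in the protocol and an unsettled choice of scale, in a study whose sample size was not set by formal hypothesis testing. Severity: minor.

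**What to change.** Reconcile Protocol 9.5.2 with the scale cited in Protocol 5.10, Protocol 7.2 and SAP 6.4.1.1. Print one contiguous set of diameter categories in both documents, with every value in exactly one grade, and state the precision to which subjects read and sites record the diameter. If the SAP is to use a scale other than 9.5.2, list that in SAP section 7. The choice of cut-points is for the sponsor; none is proposed here.

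Separately, ask the sponsor whether the Investigator's severity field is filled when the Investigator agrees with the diary. If it is not, one sentence in SAP 6.4.1.1 should say how a blank is read.

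The cost is one short list in two documents and a sentence or two in the SAP, with a small protocol clarification or a SAP section 7 entry. No new data and no extra table are needed. The change should be made before unblinding.
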